6.6.4. Use in Nursing Women

It is unknown whether pembrolizumab is excreted in human milk. Since many drugs are excreted in human milk, and because of the potential for serious adverse reactions in the nursing infant, participants who are breast-feeding are not eligible for enrolment.

6.7. Treatment of Overdose of IMP

For purposes of this trial, an overdose will be defined as any dose exceeding the prescribed dose for pembrolizumab by over 20%. Please see section 7.7 for definitions and reporting procedures.

6.8. Safety Follow-Up Visit

The mandatory safety follow-up visit should be conducted 30 days after the last dose of trial treatment or before the initiation of a new anti-cancer treatment, whichever comes first. All AEs that occur prior to the safety follow-up visit should be recorded. Participants with an AE of Grade > 1 will be followed until the resolution of the AE to Grade 0-1 or until the beginning of a new anti-neoplastic therapy, whichever occurs first. SAEs that occur within 30 days of the end of treatment or before initiation of a new anti-cancer treatment should also be followed and recorded.

6.9. Survival Follow-up

Once a participant experiences confirmed disease progression or starts a new anti-cancer therapy, the participant moves into the survival follow-up phase. Participants will not be expected to attend clinic visits during the survival follow-up but information on the participant's status will be gathered by the research team from the participant's medical notes, the participant's GP and telephoning the patients directly is applicable. The survival period will continue every 12 weeks for 3 years until death, lost to follow up, withdrawal of consent or the end of the study.

6.10. Permanent Discontinuation of Trial Medication and Withdrawal from the Study

6.10.1. Permanent Discontinuation of Trial Medication

A patient may be permanently discontinued from the trial medication for any of the following reasons:

- The subject withdraws consent.
- Confirmed radiographic disease progression

Note: For unconfirmed radiographic disease progression, please see Section 5.3.8

Note: A patient may be granted an exception to continue on treatment with confirmed radiographic progression if clinically stable or clinically improved.

- Unacceptable adverse experiences as described in Section 6.2
- Intercurrent illness that prevents further administration of treatment
- The patient has a confirmed positive serum pregnancy test
- Noncompliance with trial treatment or procedure requirements
- Administrative reasons

Trial patients will not be replaced or enrolled more than once. The primary reason for discontinuation should be recorded on the eCRF. Once the trial medication has been discontinued the patient should complete the end of treatment (if applicable) and safety follow-up visit procedures as listed in the schedule of study assessments (Table 2). After the end of treatment, patients will continue to be assessed for AE and SAE monitoring until completion of the safety follow up visit.

6.11. Withdrawal from the Study

Withdrawal from the study refers to discontinuation of both trial medication and future study visits / assessments; this can occur at any time according to the following reasons:

- Patient decision
- Lost to follow-up
- Death
- PI decision

Subjects may withdraw consent at any time for any reason or be dropped from the trial at the discretion of the investigator should any untoward effect occur. In addition, a patient may be withdrawn by the investigator if enrolment into the trial is inappropriate, the trial plan is violated, or for administrative and/or other safety reasons. When a patient discontinues/withdraws prior to trial completion, all applicable activities scheduled for the final trial visit should be performed at the time of discontinuation. Any adverse events which are present at that time should be followed in accordance with the safety requirements outlined in Section 7. Patients who a) attain a CR or b) complete 24 months of treatment with pembrolizumab may discontinue treatment with the option of restarting treatment dependant on the investigators clinical judgement. After discontinuing treatment following assessment of CR, these patients should return to the site for a safety follow-up visit and then proceed to the survival follow-up period of the study as described in the schedule of study assessments (Table 2).

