8.2. Sample Size and Power Considerations

The sample size of this study was calculated using a 2-sided α of 5%; power of 80%; RECIST response rate in the pembrolizumab arm is 30%; RECIST response rate in the pembrolizumab and radiotherapy arm is 50%. The study will randomise 234 patients in total (210 minimally required for statistical power calculation purposes, 105 patients in each arm; 20 additional patients to account for potential drop outs – an expected drop out rate of 10%) over 18 months i.e. 11-12 patients per month in approximately 15 to 24 UK centres. In the event that enrolment is slower than expected the Trial Steering Committee will consider adding additional UK sites. Patients enrolled in the trial are expected to be recruited from the routine clinics of the participating centres.

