8.4.1. Analysis populations

The efficacy results of the trial will be analysed on an intention to treat (ITT) basis. The ITT population is defined as all patients randomised in the study and are analysed as randomised for response rate, PFS and OS.

The safety data will be analysed by treatment received, irrespective of randomisation, in patients who received at least one treatment dose. Patients withdrawn prior to the first treatment dose will be excluded.

In addition, after 50% of the patients have been randomised and are evaluable for the primary endpoint an interim analysis will be carried out to assess the difference between the two trial arms. In the event that both arms showed a RECIST response rate of 30% when approximately 120 patients are evaluable then it will be judged unlikely that the pembrolizumab and radiotherapy arm will show a RECIST response rate of 50% relative to the 30% RECIST response rate in the pembrolizumab only arm at the end of the trial and the trial will be stopped.

Furthermore when 50% of the patients have been recruited this will be reviewed by the independent members of the TSC only, within a closed session. They will also decide if the results of the analysis needs to be released to the TMG, and whether any changes to the study should be implemented in terms of its continuance

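### Sections 5.1, 6.9, 6.10.1 and 6.11 conflict on whether survival status is still collected after an investigator removes a randomised patient, which exposes OS and PFS to informative censoring

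*Combined protocol and SAP*

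**What the plan says.** **6.11 (Withdrawal from the Study).** The definition is "Withdrawal from the study refers to discontinuation of both trial medication and future study visits / assessments". A PI decision is a listed reason. The text lets the investigator drop a patient for any untoward effect, and adds that "a patient may be withdrawn by the investigator if enrolment into the trial is inappropriate, the trial plan is violated", or for administrative or other safety reasons.

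**6.10.1 (Permanent Discontinuation of Trial Medication).** Unacceptable adverse experiences, "Noncompliance with trial treatment or procedure requirements" and administrative reasons are grounds to stop trial medication. The section itself promises AE and SAE monitoring up to the safety visit and says nothing about survival.

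**5.1 (Study Schedule) and 3.4 (Follow Up).** Patients who permanently stop pembrolizumab attend a safety visit 30 days after the last dose. They are then followed for survival every 12 weeks.

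**6.9 (Survival Follow-up).** Status is collected from notes, the GP or by telephone, without clinic visits, "every 12 weeks for 3 years until death, lost to follow up, withdrawal of consent or the end of the study". An investigator decision is not on that list.

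**8.4.1 and 8.4.2.** "The ITT population is defined as all patients randomised in the study and are analysed as randomised" for response rate, PFS and OS. OS without a recorded death is censored when the patient was last seen alive. PFS of patients withdrawn from follow-up is censored at the last assessment.

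**The concern.** The same event can lead to two different outcomes. A patient who stops because of an adverse effect, non-compliance or an administrative reason stays in survival follow-up if the site applies 6.10.1 with 5.1. The same patient leaves all assessments if the investigator applies 6.11. Inappropriate enrolment and violation of the plan appear only in 6.11, yet a patient removed for either remains in the all-randomised ITT set. No text says which section governs.

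The trial is open label (6.3.10), so the person making this choice knows the arm. Log-rank and Cox analyses assume that censored patients have the same future risk as those still followed. Discretionary removal puts that assumption at risk where the reason is linked to prognosis, as toxicity may be. The loss is avoidable, because survival status needs no visit.

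**Working it through.** **1. The sections side by side**

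| Reason | 6.10.1 then 5.1 | 6.11 | Ends survival follow-up in 6.9? |
|---|---|---|---|
| Adverse effect | drug stops, survival followed | may end all assessments | not listed |
| Non-compliance / plan violation | drug stops for non-compliance, survival followed | may end all assessments | not listed |
| Administrative | drug stops, survival followed | may end all assessments | not listed |
| Inappropriate enrolment | not mentioned | may end all assessments | not listed |
| Withdrawal of consent | drug stops | ends all assessments | yes |

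Three other details make the 6.11 reading plausible at a site:
- 6.11 sends patients who stop after a complete response on to survival follow-up, but says nothing similar for patients the investigator withdraws.
- 6.9 opens survival follow-up at confirmed progression or new anti-cancer therapy, so a patient withdrawn without either is not clearly covered by it.
- 3.5 counts a patient as finished on completing survival follow-up or on discontinuing the study for other reasons.

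Sections 6.4.2 (need for prohibited therapy) and 6.6.3 (pregnancy) also speak of removal from the trial or study without saying whether survival status continues.

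**2. The plan's own figure**

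The only sample-size calculation (8.2) is for the 12-week response rate: 30% against 50%, two-sided 5%, power 80%.

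- Without continuity correction: n = [1.960·√(2·0.4·0.6) + 0.842·√(0.3·0.7 + 0.5·0.5)]² / 0.2² = 1.929² / 0.04 ≈ 93 per arm.
- With continuity correction: (93/4)·[1 + √(1 + 4/(93·0.2))]² ≈ 103 per arm, close to the stated 105.
- Drop-out: 210 / (1 − 0.10) ≈ 234 (233.3 rounded up to an even total), or 117 per arm.

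These figures do not change. No OS event count, hazard ratio or power is stated, so the size of the present problem can only be illustrated.

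**3. Illustration for OS**

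Taken from the documents: 117 per arm and 36 months of follow-up (simplified to a common length). Assumed: exponential OS with a 24-month median, no true difference, and a subgroup in both arms with a multiplied hazard. In one arm only, that subgroup is censored at a uniformly distributed time in months 0–3. Removing 5% of 117 is about 6 patients; 10% is about 12. The hazard ratio is estimated as exp[(O − E)/V] from the log-rank statistic, averaged on the log scale. There were 20,000 simulated trials per row, so an error rate near 5% is known to within about ±0.3 percentage points.

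| Removed from one arm | Hazard of those removed | Mean OS HR (truth 1.00) | Two-sided error |
|---|---|---|---|
| 5% | ×1 | 1.00 | 5.2% |
| 5% | ×2 | 0.97 | 5.2% |
| 5% | ×3 | 0.96 | 5.7% |
| 10% | ×1 | 1.00 | 5.1% |
| 10% | ×2 | 0.94 | 6.3% |
| 10% | ×3 | 0.92 | 7.7% |

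With the same removals in both arms, the HR is 1.00 in every row and the error is 4.9–5.2%. With an assumed median of 12 months, one-arm removal of 5–10% at ×2–×3 gives an HR of about 0.98–0.94. The bias favours whichever arm loses the patients.

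**The case against.** The strongest reply has five parts.

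- **6.9 already answers the point.** It gives a specific list that leaves out investigator decisions and needs no visits, and assessments in 6.11 could be read as clinic assessments only. This narrows the point to a conflict between sections, but does not remove it: 5.2.5 treats survival status as something the investigator assesses, and no section is given precedence.
- **The analysis survives.** A reader might infer that the ITT analysis of OS cannot be delivered. The documents do not support that: withdrawn patients stay in the ITT set under 8.4.1 and are censored under 8.4.2, so the analysis runs. What is at risk is the validity of the censoring.
- **A one-arm effect is not shown.** A reader might infer that undelivered radiotherapy, a violation possible in only one arm, will flatter that arm. Nothing in the documents says that it leads to withdrawal. Triggers exist in the control arm too: under 6.4.2, patients needing palliative radiotherapy are to be removed. Removals could be balanced, or heavier among controls, which would reverse the bias. This stands.
- **The size is modest.** Removing 10% of an arm by investigator decision alone would use up the whole expected drop-out rate in 8.2. At 5%, the error barely moves. OS is a secondary endpoint, and 8.5 anticipates Bonferroni correction for secondary endpoints. This also stands.
- **The eCRF already records reasons** for stopping treatment (6.10.1) and for withdrawing (10.4). This is true, but it does not make a site separate stopping treatment from ending consent to follow-up.

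**Conclusion.** The contradiction is real and should be reconciled. Section 6.11, followed as written, allows a discretionary end to survival collection that 5.1 and 6.9 do not provide for. In 6.10.1 the same kinds of reason only stop the drug. Continued survival follow-up in those cases rests on 5.1 and 3.4, not on 6.10.1 itself.

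The consequence is exposure to informative censoring, not loss of the analysis. On the stated assumptions the OS hazard ratio under no effect moves to about 0.97–0.96 with 5% removed from one arm and 0.94–0.92 with 10%. The two-sided error is about 5–6% and 6–8% respectively. The median OS, the removal rates, the one-sided pattern and the excess hazard are all assumptions. Without both an imbalance between arms and a link to prognosis, there is essentially no bias, only lost events.

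For PFS the censoring rule for withdrawn patients creates the same kind of exposure, which has not been quantified here. Scheduled scans stop at the end of treatment in any case (5.3.8), so what 6.11 adds is mainly the loss of deaths without earlier documented progression.

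**What to change.** 1. In 6.11, state that withdrawal initiated by the investigator, including for ineligibility or protocol violation, does not end survival-status collection. It continues every 12 weeks through notes, GP or telephone, as in 6.9, for all randomised patients unless the patient withdraws consent to it.
2. Make 5.1, 6.9 and 6.10.1 agree with this, including the condition for entering survival follow-up in 6.9.
3. Where 6.4.2 and 6.6.3 speak of removal from the trial or study, say whether survival status continues, in line with item 1.
4. In the eCRF, record discontinuation of treatment separately from withdrawal of consent to follow-up.

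The cost is protocol wording, one eCRF field and a few remote checks of a kind the plan already provides for. The change protects OS. For PFS it recovers deaths but not missing scans. Which events should stop treatment is a clinical matter and is not addressed here.

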7.0. PHARMACOVIGILANCE

7.1. Definition of an Adverse Event (AE)

An AE is defined as any untoward medical occurrence (including deterioration of a pre-existing medical condition) in a patient or clinical trial patient administered a medicinal product and which does not necessarily have to have a causal relationship with this treatment. An AE can therefore be any unfavourable and unintended sign (including an abnormal laboratory finding), symptom (e.g. nausea, chest pain), signs (e.g. tachycardia, enlarged liver) or disease temporally associated with the use of a medicinal product or protocol-

specified procedure, whether or not considered related to the medicinal product or protocol-specified procedure.

Any worsening (i.e., any clinically significant adverse change in frequency and/or intensity) of a pre-existing condition that is temporally associated with the use of the pembrolizumab and/or radiotherapy, is also an adverse event. Changes resulting from normal growth and development that do not vary significantly in frequency or severity from expected levels are not to be considered adverse events. Examples of this may include, but are not limited to, onset of menses or menopause occurring at a physiologically appropriate time. Adverse events may also occur in screened patients during any pre-allocation baseline period as a result of a protocol-specified intervention, including washout or discontinuation of usual therapy, diet, placebo treatment or a procedure.

7.1.1. Disease Progression

Disease progression of the cancer under study is not considered an adverse event unless it results in hospitalisation or death.

7.1.2. New Cancers

The development of a new cancer should be regarded as an SAE and reported accordingly.

7.1.3. Abnormal Laboratory Test Results

All clinically important abnormal laboratory test results occurring during the study will be recorded as AEs. The clinically important abnormal laboratory tests will be repeated at appropriate intervals until they return either to baseline or to a level deemed acceptable by the investigator, or until a diagnosis that explains them is made.

7.1.4. Pregnancy and Lactation

Pregnancy and lactation are not considered adverse events, however these events should be reported to the RM-CTU following guidance in section 7.2.2.

7.2. Assessing and Recording Adverse Events

All adverse events will be recorded from randomisation until completion of the safety follow-up in the eCRF. AEs will be followed up until resolution, stability or it is clinically feasible to do so. The final outcome must not only be documented in the eCRF but also recorded in the participants medical records. Serious Adverse Events

(SAEs) will also be recorded throughout the study until the safety follow-up visit. The reporting timeframe for adverse events meeting any serious criteria is described in section 7.5

Any unresolved AEs at the patient's last visit should be followed up for as long as medically indicated, but without further recording in the eCRF. If an Investigator learns of any SAEs, including death, at any time after a patient has completed the study and he/she considers there is a reasonable possibility that the event is related to pembrolizumab, the Investigator should notify the RM-CTU.

The following details will be collected in the eCRF for each AE:

- AE description / diagnosis
- Date of onset and date of resolution
- NCI-CTCAE grade maximum intensity
- Seriousness
- Investigator causality rating against the study medication (yes or no)
- Action taken with regard to study medication
- Outcome

In addition, any adverse events occurring during the screening period that are a result of a protocol-specified intervention should also be recorded according to guidelines for standard AE reporting.

7.2.1. Evaluating Adverse Events

AEs will be evaluated by an investigator who is a qualified physician.

7.2.1.1. Determining AE Severity and Grade

AE severity and grade will be evaluated according to the NCI Common Terminology for Adverse Events (CTCAE), version 4.0 and LENT SOMA radiation toxicity grading system. Any adverse event which changes CTCAE grade over the course of a given episode should be closed at the date the severity changed and a new AE recorded on the AE e-case report forms from that date at the new severity.

Grade 1	Mild; asymptomatic or mild symptoms; clinical or diagnostic observations only; intervention not indicated.
Grade 2	Moderate; minimal, local or non-invasive intervention indicated; limiting age-appropriate instrumental ADL.
Grade 3	Severe or medically significant but not immediately life-threatening; hospitalisation or prolongation or hospitalisation indicated; disabling; limiting self-care ADL.
Grade 4	Life threatening consequences; urgent intervention indicated.
Grade 5	Death related to AE

Table 11: AE severity

7.2.1.2. Determining AE Causality

The Investigator must endeavour to obtain sufficient information to determine the causality of the AE (i.e. IMP, other illness, progressive malignancy etc.) and must provide his/her opinion of the causal relationship between each AE and IMP. This may require instituting supplementary investigations of significant AEs based on their clinical judgement of the likely causative factors and/or include seeking a further opinion from a specialist in the field of the AE.

Causality is the relationship of an AE to the IMP and will be determined as follows;

Definite:	There is clear evidence to suggest a causal relationship.
	Starts within a time related to the IMP administration and
	No obvious alternative medical explanation.
Probable:	There is evidence to suggest a causal relationship
	Starts within a time related to the IMP administration and
	Cannot be reasonably explained by known characteristics of the patient's clinical state.
Possible:	A causal relationship between the IMP and the AE is at least a reasonable possibility.
	Starts within a time related to the IMP administration
	However, the influence of other factors may have contributed to the event (e.g. the patient's clinical condition, other concomitant treatments).
Unlikely:	There is little evidence to suggest there is a causal relationship.
	There is another reasonable explanation for the event (e.g. the patient's clinical condition, other concomitant treatment).
	The time association is such that the trial drug is not likely to have had an association with the observed effect.
Not related:	The AE is definitely not associated with the IMP administered.

Table 12: Determining causality relationship of AE to an IMP

7.2.2. Reporting of Pregnancy and Lactation

It is the responsibility of investigators or their designees to report any pregnancy or lactation in a patient (spontaneously reported to them), including the pregnancy of a male patient's female partner that occurs during the trial or within 120 days of completing the trial, or 30 days following cessation of treatment if the patient initiates new anticancer therapy, whichever is earlier. All patients and female partners of male patients who become pregnant must be followed to the completion/termination of the pregnancy. Pregnancy outcomes of spontaneous abortion, missed abortion, benign hydatidiform mole, blighted ovum, foetal death, intrauterine death, miscarriage and stillbirth must be reported as serious events (Important Medical Events). If the pregnancy continues to term, the outcome (health of infant) must also be reported. Such events must be reported within 24hours of becoming aware of the event to the Sponsor by [contact] who will also inform MSD.

7.3. Definitions of Serious Adverse Events (SAE)

An SAE is an AE occurring during any part of the study that meets one or more of the following criteria:

- Results in death;
- Is life threatening; **or** places the patient, in the view of the investigator, at immediate risk of death from the event as it occurred¹
- Results in persistent or significant disability/incapacity;
- Results in or prolongs an existing inpatient hospitalisation²;
- Is a congenital anomaly/birth defect (in offspring of patient taking the product regardless of time to diagnosis);
- Is a new cancer (that is not a condition of the study);
- Is associated with an overdose (whether accidental or intentional). Any adverse event associated with an overdose is considered a serious adverse event.
- Is an important medical event that may not result in death, not be life threatening, or not require hospitalisation but may be considered a serious adverse event when, based upon appropriate medical judgment, the event may jeopardise the patient and require medical or surgical intervention to prevent such an outcome.

¹ This does not include an AE which hypothetically might have caused death if had it occurred in a more severe form.

² Hospitalisation is defined as an unexpected inpatient admission, regardless of length of stay, even if the hospitalisation is a precautionary measure for continued observation. It does not usually apply to scheduled admissions that were planned before study inclusion or visits to casualty (without admission).

